## **V. Participant Complaints**

Participants will have multiple channels for communicating potential complaints and/or requesting additional information. In addition to the phone number for the PI and the UNM IRB, which will be provided on the consent form, participants will be able to discuss complaints and/or submit them anonymously in writing to the interviewers and intervention facilitators. Furthermore, participants can also discuss any concerns with staff at the community partner organization through which they are participating. These staff will have a form for documenting concerns/complaints and submitting them confidentially to the PI.

## **STUDY DATA**

---

### **I. Data Management Procedures and Confidentiality**

All qualitative interviews will be digitally recorded (if participant agrees) and transcribed verbatim. The digital recordings will be kept on a password-protected UNM Shared Drive (which the PI already has in her lab). The only people with access to file on the Shared Drive with the digital recordings will be the PI, [name], and RA [name]. The digital recordings will be destroyed (by deleting the files) once the study is completed. The transcripts will be electronic only and will not include any identifying information. If participants use any names during the qualitative interviews, these will be changed to pseudonyms in the transcripts.

The quantitative data will be collected via Computer-Assisted Personal Interviewing (CAPI), which means it will be entered directly into password-protected laptops. Thus, there will be no paper records of quantitative data. The CAPI data will include ID numbers only and will be transferred from the laptops to the Secure Shared Drive as soon as it is collected.

The only individually identifiable private information that will be collected from participants is name, address, and phone number for tracking purposes. The PI, co-investigators, research assistants, and interviewers will have access to participants' names, addresses, and phone numbers. However, this information will be kept separate from all interview and intervention data collected. Each participant will be assigned a unique numerical identifier (five-digit ID number) and this code will be placed on the interview forms, digital recordings, and transcripts. The master list linking participants to ID numbers will be kept separate from the data set in a locked file cabinet in the PI's lab and on the PI's password protected computer. This master list will be destroyed prior to study closure.

All information will be kept confidential to the extent allowable by law. No names or identifying information will be included on interviews, digital recordings, or transcripts. We will not inquire about immigration status at any point during the study. No identifying information will be included in any reports or presentations resulting from this study. Furthermore, only general themes appearing across participants will be reported. Intervention participants will also be asked to keep all information shared in the Learning Circles confidential.

As stated on the NIH website (<https://humansubjects.nih.gov/coc/NIH-funded>), "Per Section 2012 of the 21st Century Cures Act as implemented in the 2017 NIH Certificates of Confidentiality Policy, all ongoing or new research funded by NIH as of December 13, 2016 that is collecting or using identifiable, sensitive information is automatically issued a CoC (Certificate of Confidentiality).

### **II. Data Analysis/Statistical Considerations**

Quantitative data analysis. All raw data will be examined to verify quality and identify potential outliers and distributional issues. Psychometric properties of existing scales will be verified, and psychometric analyses will be conducted on modified measures. To reduce Type I errors, data reduction (e.g., second-order confirmatory factor analysis) will be used, where feasible, to guide the combination of individual scales and variables into meaningful constructs. Significant findings on composite constructs will be followed up with parallel analyses on component variables. Additional

analyses will identify characteristics of individuals who drop out or receive lower dosage. Covariates of attrition will be used to estimate complier average causal effects. Although missing data will be minimized through use of incentives, culturally sensitive assessment, and proactive retention strategies, it is a potential problem in longitudinal research. Pattern mixture modeling will be used to determine whether missing data affect study conclusions or are “ignorable” (i.e., conditionally missing at random). Missing data determined to be ignorable will be estimated using expectation maximization and multiple imputation procedures appropriate for longitudinal data. Sensitivity analysis will be used to examine the possible impact on study conclusions involving any missing data found to be non-ignorable.

***Hypothesis 3.2*** *Participants in IWP will show lower psychological distress over time and*

***Hypothesis 3.3*** *IWP participants’ protective factors (access to resources, English proficiency, environmental mastery, social support) will increase significantly over time.* Growth curve modeling will be implemented using hierarchical linear modeling (HLM). Analyses will proceed sequentially beginning with baseline ‘intercept-only’ models, then testing fully parameterized model (see Goodkind, et al., 2012 for detailed description of analytic method). If this iterative process identifies that the best fitting model includes significant random effects corresponding to the significant fixed effects (i.e., that there is significant variability in intercepts and/or slopes), we will attempt to model it using level-2 predictors. Level-2 predictors to be tested as potential moderators will include sex, age, length of time in the U.S., and intervention hours, which will allow us to identify relevant individual difference variables (e.g., age) that may predict response to the intervention and to test whether intervention dosage predicts differential change (a finding that would strengthen the inference of treatment effects). Calculating effect sizes for multilevel models is complex; because our focus will be the effect of the intervention over time, we will examine the percentage of variance explained (PVE) by the addition of time to each model by comparing the PVE of the best fit Level 1 model to the Level 1 intercept-only model.

***Hypothesis 3.4*** *Lower levels of psychological distress will be mediated by increased access to resources, English proficiency, environmental mastery, and social support.* The mechanisms of intervention effectiveness will be examined through structural equation modeling (SEM), which will allow modeling of mediation pathways linking intervention components to primary outcomes via effects on protective factors. Multigroup SEM will provide tests of mediation effects. Latent change and latent trajectory modeling will be used to assess longitudinal mediation effects, including the effects of change from baseline to mid- and post-intervention on protective factors (e.g., access to resources, English proficiency, social support, environmental mastery) on subsequent change in primary outcomes (e.g., PTSD, depression, and culturally-specific distress symptoms over time) and parallel- or lagged-process links between change trajectories on protective factors and primary outcomes over time. Mplus software will be used for these analyses, due to its flexible estimation capabilities and ability to test specific mediation effects.

**Qualitative data analyses.** Qualitative data will contribute to addressing questions related to Aims 1, 2 and 3. For Aim 1, we will examine the participants’ perspective on how sociopolitical and policy contexts impact their psychological distress, as well as their experience and perspective on the development of protective factors and relationship of these to well-being. Aim 2 will be explored qualitatively, through conducting in-depth process evaluation case studies of local context and how these impact the adaptation and implementation at each site, facilitators and barriers, and evaluation of change resulting from the intervention. Aim 3 will be evaluated with a convergent mixed methods design; the qualitative component will serve a complementary and explanatory role in conjunction with the quantitative component to explore participant experiences in the intervention as well as change. We will employ a constructivist grounded theory approach, which is a well-known way to explicate processes, in this case change related to the intervention. Theory is “grounded” in the data themselves. Constructivist grounded theory therefore uses a combined inductive and deductive approach, coupled with the recognition that study participants and researchers ‘co-construct’ data, thus making it a good fit for community-based participatory research designs. As such, analyses are based on data derived directly from research questions and on open-ended questions that aim to allow participant perspective and meaning to be fully developed as part of the research process. A

key aspect of this approach is its iterative nature, thus analysis will be ongoing and inform the questions asked in subsequent interviews. Interviews will be professionally transcribed, then checked for accuracy, and imported into NVivo 11, a qualitative data analysis software program. [name] will lead an analysis team that includes [name], and members of each community organization. Coding of each interview will be done by two team members. The first level of analysis will involve two steps: 1) coding the content of each interview according to question so that each question can be examined across the data, and 2) text-based coding, where the coding team read the text and mark recurrent themes or statements. Thus, the initial research questions, as well as themes that emerge from the data, will be assigned codes (e.g., during analysis of data in previous studies, changing gender roles was repeatedly identified as important by interviewees, but was not originally a topic of analysis). As themes emerge, coders will meet to define and standardize them, to agree on a structural framework to elucidate the relationship of themes to each other, and to determine how they should be applied to the data. All interviews will then be coded using the coding framework. This constitutes the second level of analysis in which text is coded into thematic categories. The third level involves focused coding of prominent thematic clusters, analyzing the content of these themes for patterns and meaning. At each step, the team will meet with the CAC to engage in member checking of the analytical categories and in collaborative analysis.

Integration of mixed methods data. In a mixed methods study, the integration of quantitative and qualitative data is paramount. This study can be characterized as a convergent mixed methods design. The qualitative component in Aim 1 is formative. In Aim 2, qualitative data collected in Aim 1 will inform the adaptation, and additional qualitative data will be collected on the adaptation process, as well as on organizational readiness, capacity and how local and community context informed the adaptation and implementation of the intervention model. In Aim 3, the quantitative component is primary with an embedded qualitative component, the function of which is to provide convergence, complementarity and expansion on quantitative data for individual participants. Convergence occurs when qualitative and quantitative methods are used to answer the same research questions (e.g., how outcomes change over time). Quantitative and qualitative data will be integrated in two primary ways. First, the data will be *connected* wherein quantitative data (e.g., demographics; distress) will be incorporated into our qualitative data set to inform qualitative data collection from participants. Second, data will be *merged* to explore individual change quantitatively and qualitatively. An additional qualitative component for Aim 2 will analyze the process of adaptation and implementation of the intervention and Aim 3 will analyze multilevel outcomes related to changes in organizational, local, and state policies and practices. The PI and Co-Is will have monthly meetings throughout data collection and analysis to ensure that processes are well-integrated and findings are informing the complementary approaches.

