### **II. Participant Enrollment**

24 Latinx immigrant adult participants will be enrolled in Aim 1.

90 Latinx immigrant adult participants will be enrolled in Aim 3 to participate in the intervention and 4 interviews each.

6 organizational staff will be enrolled in Aim 3 to complete 2 qualitative interviews each.

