**Aim 3:** Aim 3 involves an intervention and 4 individual interviews with each participant. The Immigrant Well-being Project (IWP) Intervention Model is a 6-month intervention with two main components: 1) Learning Circles. Learning Circles (LCs) occur once per week for six months (total of 24 LCs). Each meeting is two hours and includes immigrants and undergraduate paraprofessionals. LCs have two parts: cultural exchange and one-on-one learning. Cultural exchange occurs for the first hour and is facilitated together by one undergrad and one immigrant who choose the topic. To enable all participants to share in the discussion, interpreters are present. Cultural exchange provides a forum for immigrants and undergrads to learn from each other, share ideas, develop plans for collective action, and realize the important contributions they are capable of making. The second component of the LCs is one-on-one learning. For the last hour, immigrants and undergrads work in pairs. During one-on-one time, immigrants direct their own learning (e.g. English, job applications). 2) Advocacy. Advocacy begins after the first two weeks of LCs. For the remaining 5½ months of *IWP*, undergrads spend an additional 4-6 hours each week (outside of the LCs) with their immigrant partner(s) to engage in advocacy together around any issues the immigrant(s) would like to address. They follow a 4-phase process (assessment, implementation, monitoring, and secondary implementation) for each unmet need or goal. Undergrads also work to transfer advocacy skills to their partner, through shared engagement in advocacy, modeling, and role plays. The *IWP* employs a holistic approach that integrates advocacy and learning to address multiple needs of immigrants (i.e., English proficiency, access to resources, understanding of their environment, social support, valued social roles). However, rather than emphasizing only what immigrants need to learn to survive in the U.S., the *IWP* focuses on

**mutual learning**, through which immigrants both learn from and teach people born in the U.S.

Quantitative interview procedure. Each participant will complete 4 quantitative interviews: pre, mid (~3 months after pre), post (~6 months after pre), and follow-up (14 months after pre). The 1-1½ hour

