### III. Participant Withdrawal

Participants are free to withdraw at any point from the study. If a participant indicates their desire to withdraw from the study, we will not collect any further interview data from the participant. Any data collected previously from a participant who withdraws from the study will be destroyed [removed from the SPSS (quantitative) and NVivo (qualitative) databases and not included in analyses].

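### MNAR sensitivity analysis is made conditional on an ignorable/non-ignorable classification that observed data cannot settle; it should be prespecified and always run

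*Combined protocol and SAP*

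**What the plan says.** The missing-data strategy is in the combined protocol and SAP, Study Data, section II (Data Analysis/Statistical Considerations). It has three steps.

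1. Pattern-mixture modelling comes first, without condition. It "will be used to determine whether missing data affect study conclusions or are “ignorable” (i.e., conditionally missing at random").
2. Data judged ignorable are filled in: "Missing data determined to be ignorable will be estimated using expectation maximization and multiple imputation procedures appropriate for longitudinal data". No sensitivity analysis is attached to this branch.
3. Data judged otherwise go to a further check: "Sensitivity analysis will be used to examine the possible impact on study conclusions involving any missing data found to be non-ignorable".

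No test, threshold, identifying restriction or range of departures from MAR is given for any step.

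The analyses affected are those of Hypotheses 3.2 (distress falls over time) and 3.3 (protective factors rise over time). For these, "Growth curve modeling will be implemented using hierarchical linear modeling (HLM"). There is one intervention group: "90 Latinx immigrant adult participants will be enrolled in Aim 3 to participate in the intervention and 4 interviews each". Interviews are at "pre, mid (~3 months after pre), post (~6 months after pre), and follow-up (14 months after pre").

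Section III (Participant Withdrawal) adds: "Any data collected previously from a participant who withdraws from the study will be destroyed". Those records are also kept out of the analyses.

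**The concern.** Whether data are ignorable depends on the distribution of the unseen values given the seen ones. The observed data carry no information on that, so no model fitted to them can return a finding of ignorable or non-ignorable. A step whose output is that finding, and whose output decides whether an MNAR analysis is done, is an invalid rule as written. It is more than a missing detail.

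The design makes this matter. Both hypotheses concern change within one group, and no comparison arm exists in which similar attrition might partly cancel. If those lost are doing worse than MAR predicts, the loss shows up directly as improvement. If they are doing better, improvement is understated. Either way, a reader would want the conclusions stress-tested whatever the classification said.

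**Working it through.** **Inputs from the documents.** N = 90, one group; interviews at 0, 3, 6 and 14 months; growth-curve model. The documents state no dropout rate, alpha, effect size or variance, so there is no figure of the plan's own to reproduce. Everything else below is assumed.

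**Step 1: can observed data classify?** Write the joint distribution as f(y_obs, r) × f(y_mis | y_obs, r), where r is the dropout pattern. In a delta-adjusted pattern-mixture model, delta enters only the second factor. The observed-data likelihood is the same for every delta, including delta = 0 (MAR). The data therefore cannot choose between them.

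**Step 2: size at one visit.** Let a fraction d be missing, with true mean delta SD away from the MAR prediction. Then true mean = MAR mean + d × delta.

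- d = 0.20, delta = 0.2: 0.04 SD
- d = 0.20, delta = 0.5: 0.10 SD
- d = 0.30, delta = 0.2: 0.06 SD
- d = 0.30, delta = 0.5: 0.15 SD

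For scale, with visit SD 1 and an assumed between-visit correlation of 0.6, the SE of a mean change in 90 people is √(2 × (1 − 0.6)/90) = √(0.8/90) ≈ 0.09 SD. The shifts are about 0.4 to 1.6 SE (0.04/0.094 and 0.15/0.094). The effect on a fitted slope depends on how delta is spread over visits.

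**Step 3: how might a classification behave?** The plan gives no rule, so two plausible ones were simulated, 3,000 runs per scenario. Each is a two-sided 5% comparison of completers with dropouts: pattern-by-time (1 df), or pattern plus pattern-by-time (2 df). Assumed variances: intercept 0.6, slope 0.04 (time in units of 6 months), residual 0.4, covariance treated as known. True slope: −0.150 SD per 6 months. Apart from the completely random case, dropout was logistic and more likely at higher (worse) scores or with larger increases.

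| Dropout depends on | Flagged at 15% dropout (1 df / 2 df) | Flagged at 30% dropout (1 df / 2 df) | Mean slope under MAR analysis (15% / 30%) |
|---|---|---|---|
| nothing | 5% / 5% | 4% / 5% | −0.150 / −0.150 |
| previous score (MAR) | 17% / 80% | 25% / 96% | −0.150 / −0.149 |
| current unseen score, moderate (MNAR) | 4% / 16% | 5% / 26% | −0.161 / −0.174 |
| current unseen score, strong (MNAR) | 5% / 46% | 4% / 68% | −0.170 / −0.193 |
| change to current unseen score (MNAR) | 15% / 17% | 22% / 27% | −0.173 / −0.196 |

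Under MAR dropout on the previous score, the estimate is about unbiased, yet the flag goes up in 17–25% (1 df) or 80–96% (2 df) of trials. Under MNAR, improvement is overstated by 7% (0.011/0.150) to 31% (0.046/0.150), yet the flag goes up in only 4–22% (1 df) or 16–68% (2 df). A flag does not indicate bias, and its absence does not indicate safety.

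**Step 4: formal withdrawers.** Section II also plans to describe the characteristics of people who drop out. For anyone whose records are destroyed under section III, neither that description nor the pattern-mixture model is possible. This covers people who state that they want to withdraw, not those simply lost to follow-up.

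**The case against.** The strongest reply is that the pattern-mixture step is unconditional, and that its first stated purpose is to learn whether missing data change the conclusions. Run with explicit identifying restrictions or delta shifts, it would itself be an MNAR check. This stands in part: a reader might infer that no MNAR check is planned at all, and the text does not support that. But the plan states no restrictions or shifts, and it uses the model's result to route data to imputation or to sensitivity analysis.

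A reader might also infer that the sensitivity analysis will almost never run when needed. The documents do not support that either. They give no decision rule, and the flag rate under MNAR ranged from 4% to 68% across the assumed tests and mechanisms. A rate near 5% would follow by construction if shifts were applied only to unseen scores and dropout was otherwise unrelated to observed ones, because the observed data would then be unaffected.

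The shifts in Step 2 are likewise arithmetic on assumed values, and the low end is under half a standard error. Nothing in the documents shows that people doing worse are the ones who leave, and nothing says the results would be presented as robust without qualification. The planned description of dropouts is useful, but it too rests on observed data and cannot establish ignorability.

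**Conclusion.** The concern holds in this form: the further sensitivity analysis depends on a classification that observed data cannot deliver, so it may be omitted when the estimates are biased and triggered when they are not. How often cannot be stated from the plan.

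The possible size is d × delta at a visit, or 0.04–0.15 SD for d of 20–30% and delta of 0.2–0.5 SD. In the simulated MNAR scenarios the slope was overstated by 7–31%. All of this rests on assumed dropout, departures and variances; the direction would reverse if people doing better were the ones lost. The identification argument in Step 1 needs none of these assumptions. The point is worth correcting before analysis. It does not show that the trial's results will be wrong.

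**What to change.** - Remove the ignorable/non-ignorable classification as a condition for anything.
- Keep the planned growth model, or multiple imputation, under MAR as the main analysis.
- Always run a delta-adjusted pattern-mixture analysis over a prespecified range, for example 0.1 to 0.5 SD in steps at 3, 6 and 14 months.
- For Hypothesis 3.2, shift missing distress scores upward. For Hypothesis 3.3, shift missing protective-factor scores in the unfavourable direction, set scale by scale, since the measures of difficulty and of satisfaction with resources appear to run opposite ways.
- Report the delta at which each conclusion changes.
- Separately, report how many participants had their data destroyed on withdrawal, and reconcile section III with the planned description of dropouts. With no retained records to shift, the delta analysis cannot recover these people.

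The cost is a change of analysis wording and a few extra model runs. Sample size, visits and participant burden are unchanged. The results may look slightly less robust.

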#### IV. *Informed Consent Process*

Latinx immigrant participants will read a consent form that explains the nature and purpose of the interview and/or intervention, ensures confidentiality, describes the participant compensation, and makes clear that participation is completely voluntary and may be terminated at any time. Participants will be made aware that they are free not to answer any question and/or to stop at any time without negative consequence. Each potential participant will be provided the consent form in Spanish or English (whichever they prefer) in advance of the interview. The consent form will also be read aloud to each potential participant, since some participants may not be literate. The consent form will be explained in detail, emphasizing the individual's right to choose not to participate. It will be clearly stated that the individual will not be penalized in any way for choosing not to participate, and refusal to participate will in no way affect the individual's access to services at the community organization which is coordinating recruitment or any services to which he or she is otherwise entitled. Next, each potential participant will be asked if they have any questions regarding the study. Each potential participant will be given adequate time to consider whether they want to participate in the study. The participants will then verbally indicate their consent (which will be documented by signature of study team member but will not require the participant's signature in order to protect confidentiality) and will be given a copy of the consent form to keep before the interview begins. A **waiver of consent documentation (no signature)** is being requested because a signed consent form would be the only record linking the participant and the study, and breach of confidentiality would be the principal risk, due to the potential situation in which some participants may not have legal status in the United States.

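### An association between intervention hours and change is counted as support for a treatment effect, although hours are not assigned and the association can arise without any effect

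*Combined protocol and SAP*

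**What the plan says.** The growth-curve paragraph for Hypotheses 3.2 and 3.3 (Study Data, section II, Data Analysis/Statistical Considerations) states: "Level-2 predictors to be tested as potential moderators will include sex, age, length of time in the U.S., and intervention hours". One stated purpose is "to test whether intervention dosage predicts differential change (a finding that would strengthen the inference of treatment effects". These predictors are tried only if the best-fitting model shows significant variation in intercepts or slopes.

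Other sections fix how hours come about:

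- **One group.** Study Design, section II (Participant Enrollment): "90 Latinx immigrant adult participants will be enrolled in Aim 3 to participate in the intervention and 4 interviews each". No comparison arm and no assignment of dose is described.
- **Voluntary participation.** Section IV (Informed Consent Process): the consent form "makes clear that participation is completely voluntary and may be terminated at any time".
- **Advocacy topics.** Section V (Data Collection Procedures) leaves the choice of topic to the participant; pairs "engage in advocacy together around any issues the immigrant(s) would like to address".
- **Scheduled dose.** Same section: "Learning Circles (LCs) occur once per week for six months (total of 24 LCs", at two hours each. Advocacy starts in the third week and has its own weekly allotment: "undergrads spend an additional 4-6 hours each week (outside of the LCs) with their immigrant partner(s".
- **Outcome times.** Same section: baseline, about 3 months, about 6 months, and 14 months.
- **Sites.** Section VI (Study Timelines): three waves, each at a different partner organization.

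**The concern.** In a randomized dose comparison, a dose-response speaks to causation because dose was set independently of prognosis. Here the hours a person accumulates depend on whether that person keeps coming, on the student partner's availability, and on the site. Each of these can be tied to how the person would have fared anyway. Someone who is already improving, or whose work and housing are stable, may attend more, and this yields a dose-response with no treatment effect. Someone with many unmet needs may use more hours and improve less, and this can hide or reverse a real one.

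Timing adds to the problem. Hours accrue during the same six months in which the pre, mid and post interviews are taken, so early change can drive later hours.

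The section on benefits foresees national dissemination if effectiveness, among other things, is demonstrated. The plan has already said that a positive dosage result would count in favor of an effect, so the wording affects what the trial may conclude.

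**Working it through.** **Scheduled dose.** Learning Circles: 24 × 2 = 48 hours. Advocacy, taking the 24 weeks less the first two: 22 × 4 = 88 to 22 × 6 = 132 hours. Total: 136 to 180 hours. The schedule is common to all, so totals well below it mainly reflect attendance and staying in.

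**Does the plan repair the comparison?**

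- Sex, age and time in the U.S. do not address reverse causation, baseline need or site.
- Characteristics of low-dose participants are to be described, but no step carries them into the hours-by-slope test.
- A complier average causal effect is planned. With no comparison arm there is no untreated outcome for would-be compliers.
- Data of participants who withdraw are destroyed (Study Data, section III), which probably trims the low-dose end selectively.

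**Size of a false association.** The plan gives no alpha, SD or correlation, so there is no figure to reproduce. The following are assumptions: two-sided 5%, complete data on n = 90, no effect of hours, zero-mean individual slopes with SD S over 14 months, residual SD e, and correlation ρ between hours and the underlying trend.

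1. Visits at 0, 3, 6, 14 have mean 5.75. Sum of squared deviations = 33.0625 + 7.5625 + 0.0625 + 68.0625 = 108.75.
2. Reliability of a person's fitted slope: (S/14)² / [(S/14)² + e²/108.75].
3. Observed correlation r = ρ × √reliability.
4. Rejection rate ≈ Φ(atanh(r) × √87 − 1.96).

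Example with S = 0.5, e = 0.7, ρ = 0.3: 0.001276 / (0.001276 + 0.004506) = 0.221, with square root 0.470. Then r = 0.141, and Φ(0.1418 × 9.327 − 1.96) = Φ(−0.64) = 26%.

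| S | e | √reliability | ρ = 0.2 | ρ = 0.3 | ρ = 0.4 |
|---|---|---|---|---|---|
| 0.5 | 0.7 | 0.470 | 14% | 26% | 43% |
| 0.5 | 0.5 | 0.597 | 20% | 39% | 62% |
| 0.8 | 0.7 | 0.648 | 23% | 45% | 70% |
| 0.8 | 0.5 | 0.766 | 30% | 59% | 84% |

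Simulation agrees to within about a percentage point and gives about 5% at ρ = 0.

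**Applying the plan's conditions (simulation, ρ = 0.2/0.3/0.4).**

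- Significant slope variance required: at S = 0.5, e = 0.7 the rates fall to about 6/11/19%. At S = 0.8, e = 0.7 they fall only to about 21/42/65%. At S = 0.8, e = 0.5 the condition is nearly always met and the upper end stays at about 84%.
- A significant mean time effect also required, with no secular trend: a zero mean passes about 5% of the time, so the highest rate becomes about 0.05 × 84% ≈ 4%.
- Both conditions, with a secular mean trend of 0.4 SD: about 6-80%.

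Larger slope variation raises the rates. With 0.5 SD per 6 months (0.5 × 14/6 = 1.17 over 14 months) and e = 0.5, the unconditional rates are about 39/70/92%.

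**The case against.** The case for leaving the text alone is that it makes a modest claim. It says a dosage finding would strengthen an inference, not establish it. Hours are one of four candidate moderators, no hypothesis is built on them, and the test is conditional. The percentages follow from a correlation that was assumed, and no passage supports any particular value. All of this is true and limits the size of the point. It does not make the claim correct: with unassigned hours and one arm, a positive result does not separate an effect from its alternatives.

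Several stronger readings are tempting, and the documents do not support them.

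- *Dosage is the only evidence of attribution offered.* The plan also lists complier effects, mediation models with lagged links, and qualitative data on change. The dosage test is the one it expressly says would support treatment inference.
- *Advocacy hours follow need.* The text lets the participant choose the topics, while weekly time is scheduled at 4-6 hours. That high-need participants use more hours is a possibility, not a documented fact.
- *Hours are known only after most of the change.* Dosing ends at month 6 and 8 of the 14 months follow it. No passage says when change occurs.
- *A null would be read as evidence against the program.* No passage says so.
- *The rates above are this plan's error rate.* They depend on assumed values and on how the conditional step is read. The sentence mentions significant random effects that correspond to significant fixed effects, then glosses this as variability alone, so it is unclear whether a significant mean effect is required.

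**Conclusion.** The point holds as a fault in the stated inference. Because hours are neither assigned nor compared with an untreated group, and overlap in time with three of four outcome measurements, an hours-by-time association would not by itself favor a treatment effect, and its absence would not count against one. That hours are partly self-selected is inferred from voluntary participation and the absence of dose assignment. Student availability and site may also drive hours, but they do not make dose independent of prognosis.

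The artifact can be large under modest assumptions: about 14-84% without the slope-variance condition and about 6-84% with it, for the ranges shown. It is about 4% or less if a significant mean effect is also required and there is no secular trend. Its actual size cannot be known from the documents. The change is worth making because it alters what the trial may claim at almost no cost; it does not call the growth-curve analysis itself into question.

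**What to change.** 1. Delete the parenthesis, or replace it with a statement that the dosage analysis is exploratory and associational and will not be used as evidence for or against effectiveness.
2. Add site/wave and baseline resource need to the dosage model; the pre interview already includes two resource scales. Account for baseline distress through the intercept-slope covariance, for example, so that the first outcome value is not also entered as a covariate.
3. Confirm whether hours are logged by date, which the documents do not say. If they are, add three sensitivity checks: pre-to-mid hours predicting mid-to-post change; total hours predicting change from month 6 to month 14; and whether pre-to-mid change predicts later hours.

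The checks in item 3 reduce reverse causation but leave common causes such as motivation or stability. With a persistent common cause, ρ = 0.3, slope SD 0.5-0.8 and residual SD 0.6 (all assumed), the first check still rejects in about 6-9% of trials, and part of that drop is lost precision. They should therefore supplement total hours rather than replace them.

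Cost: a change of wording and a few model terms, with no new visits or participants. A supportive claim is given up, and the lagged checks are less precise because each uses only part of the dose or of the follow-up.
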